10.2 Inclusion/Exclusion Criteria

Inclusion criteria

- Subjects with ET diagnosed by a Movement Disorder Neurologist aged 21 and older
- Subjects on a stable dose of tremor medication for a period of at least 6 weeks prior to screening
- Subjects with upper limb tremors
- Subjects with a minimum score of 2 on the TETRAS Question 2.4 (amplitude of at least 1-3cm)

Exclusion criteria

- Subjects with significant non-ET related abnormal findings on neurological exam.
- Subjects with a tremor at rest.
- Subjects with a diagnosis of mild cognitive impairment or dementia
- Subjects who are pregnant or nursing, or suspect that they might be
- Women of childbearing potential unable or unwilling to use a form of contraception during course of the trial
- Subjects on medications known to interact with cannabinoid-type agents
- Subjects with a history of alcohol use disorder (based on DSM-5 criteria) or substance abuse.
- Subjects with exposure within the past 21 days to primidone or within the past 7 days to benzodiazepines, ketoconazole, ritonavir, clarithromycin, rifampin, carbamazepine, St. Johns Wort, digoxin or other agents known to be strong inducers or inhibitors of CYP3A, CYP2C19, and CYP2C9.
- Subjects unwilling to abstain from consumption of grapefruits, grapefruit juice or grapefruiting-containing products that are known to strongly inhibit CYP3A4.
- Subjects taking concomitant medications that are highly protein-bound with a narrow therapeutic index (e.g. warfarin, cyclosporine, and amphotericin B).
- Subjects who do not wish to take a cannabis-derived agent
- Subjects who an allergy or sensitivity to sorbitol, xylitol, stevia or other natural sweeteners
- Subjects with an allergy or sensitivity to cannabis.
- Subjects actively using cannabis or a cannabis-derived product (within 4 weeks of screening) or who are unwilling to discontinue its use during the course of the study.
- Subject with a history of significant Axis I psychiatric disorder (e.g., mania, bipolar depressive disorder, schizophrenia, schizoaffective disorder, or other major psychiatric disorder)
- Subject with active or prior history of suicidal ideation and/or behavior.
- Subject with significant coagulopathy, immunologic, gastrointestinal, respiratory, cardiovascular (e.g., uncontrolled hypertension, myocardial infarction in the last 18 months, significant bundle branch block, congestive heart disease), or endocrine (e.g., uncontrolled diabetes, hyperthyroidism) disorder
- Subject with current or chronic infection.
- Subject with renal insufficiency (GFR <60)

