This situation arises from lack of knowledge about the cause of ET, so that clinical trials on medications have been performed on the basis of guess-work or serendipity, with the majority ending with a negative result. The lack of any new positive recommendations by the 2011 Academy of Neurology evidence-based guideline update on the treatment of ET attests to the poor yield of present approaches to drug discovery (Zesiewicz et al., 2011).

The lack of knowledge about the etiology of ET is clearly a barrier to drug discovery. However drug discovery has proceeded for other neurological conditions in which the precise etiology is not clear, such as epilepsy, migraine and multiple sclerosis. We suspect that another barrier to drug discovery for tremor is the underappreciation by pharmaceuticals of the social, economic, and clinical significance of ET. Given that half of ET persons aged 65 and over take medication for tremor (Louis et al., 2000), and 2012 demographic data that, among the 1,006.9 million persons living in the European Union, the United States, Japan, Canada, Australia and New Zealand, 163.7 million persons are aged 65 years and over, it can be estimated that 3.8 million persons in this age group in these countries are seeking or receiving medication for ET. If they are willing to pay \$4 a day to treat their tremor, the market size would be \$5.5 billion per year. Given that persons under age 65 are not included in this calculation, and another 2-3 billion persons in Asia, Latin America, Africa and the Middle East have joined or will soon join the middle class, the market size is likely much greater, at \$10-15 billion per year world-wide. Any new ET medication that is highly effective and well tolerated will likely soon dominate a large market.

In addition to neurologists empirically identifying potential treatments for tremor, ET patients themselves have empirically sought remedies. Numerous patients have identified low-dose alcohol as more effective than any prescribed ET medication for tremor suppression. Of particular interest, many ET patients have identified marijuana as more effective and well-tolerated for tremor than any prescribed ET medication, as discussed in the next section.

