Deep cerebellar nuclei (DCN) The excitatory DCN neurons are the sole output neurons of the cerebellum, and in ET tremor an oscillatory loop involves DCN-motor thalamus-motor cortex-IO/pons-cerebellum. It is thus not surprising that strokes that severely damage the DCN, motor thalamus, frontal white matter or internal capsule can eliminate tremor in ET patients (Dupuis et al., 2010). The participation of DCN in tremor is demonstrated by PET imaging in ET and by c-fos imaging in rodents given the tremorigenic drug harmaline. Interestingly, partial lesions of the DCN produce action tremor in patients with head trauma and tremor in rats after chemical DCN lesions. An extensive literature has documented that action tremor ensues after lesions of DCN in monkeys (Gemba et al. 1980). Thus the DCN may be involved in both the initiation and propagation of the oscillations that underlie tremor.

Cerebellar cortex *Pcd* mice that lose all Purkinje neurons still respond to harmaline with tremor, but the tremor is of lower amplitude and frequency compared to wild-type, indicating that Purkinje cells have a role in amplifying tremor. PET scans in ET patients demonstrate increased blood flow in the cerebellar cortex, present at rest, and increased with tremor. This increase is abolished by alcohol (Boecker et all, 1996). In the harmaline model, granule cells express c-fos early. Strokes involving the pons, which interrupt mossy fiber projections to granule cells, abolish tremor in ET (Dupuis et al., 2010). In summary, the components of the cerebellar cortex appear to be important for the amplification of hyperoscillations that underlie action tremor.

How might cannabinoids affect tremor in ET? Endocannabinoids are released by post-synaptic neurons to act retrogradely on pre-synaptic cannabinoid receptors to modulate the release of excitatory and inhibitory

neurotransmitters. The CB1R is intensely expressed on the terminals of parallel fibers derived from granule cells that contact Purkinje cells. CB1Rs are also expressed on terminals of basket and stellate interneurons, and on climbing fibers, all projecting to Purkinje cells. The Purkinje cells themselves do not express CB1Rs. Aside from the rubro-olivary projection to inferior olive, there is little CB1R expression in the DCN or inferior olive. CB2Rs are also expressed in the terminals of parallel fibers and

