9.3 Description of Screening and Study Design

SCREENING VISIT

After being screened for inclusion/exclusion criteria and providing informed consent, subjects will undergo a complete neurological examination to confirm their diagnosis of ET and exclude other neurological disorders. Additional measures collected during this visit are listed in Appendix 1. Note that subjects will need to have been on a stable dose of their medications for a minimum of 6 weeks prior to the screening visit and will be

encouraged to remain on these doses for the remainder of the study period. Subjects will be asked about their other tremor medication doses at each follow-up visit to confirm stable doses.

VIDEOTAPED TETRAS

As part of each study visit (1-3), subjects will complete a TETRAS rating scale while being videotaped. This is intended for rating purposes by two blinded raters at the completion of the study.

RANDOMIZATION

After completion of the screening visit, subjects will be assigned to one of two possible treatment arms based on a pre-set randomization matrix. Only the research pharmacy who will be responsible for dispensing the doses will be aware of which of two treatment options will be provided, but not the identity of the particular agent. The equivalence of the THC/CBD and Placebo will be equally matched by the manufacturer, making it difficult for the subject to discriminate which arm they are on. Subjects will be asked which arm they are receiving at each assessment visit and on telephone follow up to assess for potential unblinding.

DOSE TITRATION AND TREATMENT

On visit 1 and 5, subjects will receive 1 capsule of IMP every morning. On visit 2 and/or 6, if the subject tolerated 1 capsule then they would receive 2 capsules every morning. Alternatively, if 1 capsule was not tolerated, the timing of the administration would be changed to 1 capsule in the evening. At visit 3 and/or 7, if the single nightly capsule was not tolerated, the subject would be dropped at this visit. If the 2 capsules every morning were tolerated, the subject would then receive 2 capsules in the morning and 1 capsule in the evening. If 2 capsules in the morning were not tolerated, the subject dosing would be changed to 1 capsule in the morning and 1 capsule in the morning and 1 capsule nightly. Subjects will remain on the highest tolerable dose for the duration of the period until visit 4 or 8 (See Appendix 2).

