9.6 Outcome Measures

Primary Outcome Measures

The primary outcome measures will be change from baseline of tremor power by digital spirography for drug vs. placebo.

Secondary Outcome Measures

The secondary outcome measures will include the TETRAS, CGI, PRO-CTCAE, plasma concentrations of CBD/THC, Common Toxicity Criteria for adverse effects, and Columbia-Suicide Severity Rating Scale.

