APPENDIX 1: STUDY OVERVIEW

EVENT	VISIT 0: SCREENING	VISIT 1: DOSE TITRATION	VISIT 2: PK	VISIT 3: PK	TREATMENT PHASE	VISIT 4: ASSESSMENT	TAPER	WASHOUT	VISIT 5: DOSE TITRATION	VISIT 6: PK	VISIT 7: PK	TREATMENT PHASE	VISIT 8: ASSESSMENT	TAPER	TELEPHONE FOLLOW-UP	TOTAL DAYS
TOTAL DAYS	0	ų	5	1	16	1	5	22	ų	5	1	16	1	5	1	77
DAY NUMBER (±3)	0	1	3	6		22	23	28	50	52	55		71	72	77	
Consent	х															
Neurological Exam	х					x							х			
Vital Signs	х	х	Х	x		х			х	х	x		х			
TETRAS (video)	х					х							х			
Spirography	Х					X							Х			
Accelerometry	Х					Х							Х			
CGI/PGI						Х							Х			
PRO-CTCAE	х	x	х	x		х			x	х	x		х		х	
C-SSRS	Х					Х							Х		Х	
Lab Testing - pregnancy, CBC, CMP, Drug screen	x					x							x			
EKG*	x	x	x	x		x			x	x	x		x			
PK Sample(s)			Х	x		X				x	х		х			

* EKG at screening, then post-dose at each subsequent visit.

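### Ordinary alcohol use is neither restricted nor recorded before the one spirography reading per period, although the protocol reports that patients find alcohol a strong tremor suppressant

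*Combined protocol and SAP*

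**What the plan says.** **Alcohol and tremor.** Section 7.1 gives patients' experience: "Numerous patients have identified low-dose alcohol as more effective than any prescribed ET medication for tremor suppression". Section 7.3 describes raised blood flow in the cerebellar cortex in essential tremor and adds: "This increase is abolished by alcohol". It also cites imaging of the inferior olive after alcohol.

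**Rules on intake.** The only alcohol rule is an exclusion in section 10.2: "Subjects with a history of alcohol use disorder (based on DSM-5 criteria) or substance abuse". The same list is stricter about other intake. It excludes "Subjects unwilling to abstain from consumption of grapefruits, grapefruit juice", requires cannabis to be stopped for the study, and sets look-back windows for primidone and benzodiazepines. Section 9.3 standardises the meal at dosing visits. On concomitant treatment it says: "Subjects will be asked about their other tremor medication doses at each follow-up visit to confirm stable doses". Alcohol is not mentioned there.

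**Measurement.** Section 9.6 states: "The primary outcome measures will be change from baseline of tremor power by digital spirography for drug vs. placebo". Appendix 1 marks spirography at screening (Visit 0), at the visit headed "VISIT 4: ASSESSMENT", and at Visit 8. That gives one baseline and one on-treatment reading per period.

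**Analysis.** Section 9.8 plans paired t-tests with each subject as own control. It has no alcohol covariate and no rule for excluding an affected reading.

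**The concern.** The protocol gives its own reason to treat alcohol as a short-acting influence on the primary outcome, yet it controls grapefruit, cannabis, meals and tremor drugs and leaves alcohol open. The exclusion removes people with a disorder. It does not remove ordinary drinkers or those who sometimes use alcohol for their tremor.

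With one spirography reading per period, a reading taken under alcohol cannot be averaged against a clean one. Because intake is not recorded, such a reading cannot be identified later, so no sensitivity analysis could repair it.

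Two consequences are possible. If drinking is unrelated to period, it widens the spread of the paired differences. If it differs between periods, for instance because tremor is less controlled on placebo, it shifts the mean difference. With 14 to 16 pairs, a few such readings carry weight.

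**Working it through.** **Inputs from the documents.** Section 9.7: difference 15%, SD 10%, power 0.80, alpha 0.01 or 0.05, at least 14 completers, 16 planned to complete. Section 9.8: paired t-test. Appendix 1: one spirography reading per period.

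**Inputs not in the documents (assumptions).** The size of alcohol's effect on spirography, A, in points on the same scale as the 15%; the share of subjects who drink before the visit in each period; and the SD of the paired difference. Section 9.7 does not say whether its 10% belongs to one reading or to the difference, so two values are used: 10, and 10 × √2 = 14.1 (uncorrelated periods).

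**Step 1: the plan's own figure.** A two-sample normal formula at two-sided alpha 0.05 gives n per arm = 2 × (1.96 + 0.84)² × (10/15)² = 6.98, so 7 per arm and 14 in total. A paired t-test at two-sided alpha 0.01 with SD of the difference 14.1 also gives 14. The stated 14 is reproduced, but it neither supports nor refutes the alcohol point.

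**Step 2: shift of the mean.** If k of 16 subjects are affected at the placebo visit only, the mean difference moves by k × A / 16.

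- k = 1: 20/16 = 1.25 points; 50/16 = 3.1 points.
- k = 3: 60/16 = 3.75 points; 150/16 = 9.4 points.

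**Step 3: power.** Simulated two-sided paired t-test, alpha 0.05, 14 completers, true difference 15. Without alcohol, power is 0.999 (SD 10) or 0.956 (SD 14.1).

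| A | Share drinking, placebo / drug | Expected difference | Power, SD 10 | Power, SD 14.1 |
|---|---|---|---|---|
| 15 | 25% / 25% | 15 | 0.97 | 0.87 |
| 15 | 50% / 50% | 15 | 0.95 | 0.84 |
| 30 | 25% / 25% | 15 | 0.70 | 0.61 |
| 15 | 25% / 0% | 11.25 | 0.89 | 0.70 |
| 15 | 50% / 0% | 7.5 | 0.53 | 0.37 |
| 30 | 25% / 0% | 7.5 | 0.37 | 0.29 |

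The expected difference is 15 − A × (share on placebo − share on drug). Equal use leaves it at 15 and only adds spread. At alpha 0.01 power is lower throughout: for A = 15 and 25% / 0% it is 0.68 or 0.42.

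**Step 4: the baseline.** Both periods use the Visit 0 reading, so (drug − baseline) − (placebo − baseline) = drug − placebo, and an affected baseline cancels. If change is expressed as a percentage, the baseline stays only as a common divisor. It does matter for the separate comparisons with baseline in section 9.8.

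**The case against.** The strongest reply is that the practical risk is small.

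- **Visit conditions.** Section 9.3 advises dosing each morning after breakfast, section 8 sets 4-hour visits, and Appendix 3 takes a trough sample on Day 22 followed by one at 1 to 4 hours after the dose. A drink just before the reading would probably have to precede breakfast. This stands as a reason to expect few cases. It does not close the gap, because the clock time of spirography is not stated and the evening before is uncontrolled.
- **Drug screen.** Appendix 1 lists one at Visits 0, 4 and 8. Alcohol is not named and no action follows from a result. Consent pages are not in the available text, so an instruction there cannot be ruled out.
- **Magnitude.** The 20 to 50 points and the placebo-only drinking are assumptions. With three of 16 subjects affected on placebo only at 20 points, power stays at 0.95 (SD 10) or 0.76 (SD 14.1). It collapses only towards the upper end of the range. This stands.
- **Pilot status.** Section 6 describes a pilot meant to decide whether larger studies are warranted. That lowers the stakes, but the remedy is also small.

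A reader might infer that the protocol itself asserts alcohol's superiority. It reports patients' experience, and the imaging concerns blood flow and glucose use, not tremor size. A reader might also infer that any bias must run towards no difference. That needs more drinking on placebo and a tremor-lowering effect at the time of the reading. The documents show neither, and the direction of any next-day effect is not given. Nor can the point be extended to the sedation ratings of Hypothesis 2: PRO-CTCAE is also collected at Visits 1 to 3, at Visits 5 to 7 and by telephone, which a rule around the tremor visits would not reach.

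**Conclusion.** The gap is real and modest: a cheap improvement. Alcohol is presented in the background as a tremor suppressant, yet ordinary use before the one spirography reading per period is neither limited nor recorded. Under the assumed 20 to 50 points, each subject affected at the placebo visit only moves a 16-pair mean by 1.25 to 3.1 points against the 15% target. Similar use in both periods costs little power at a 15-point effect and becomes costly near 30 points. Frequency, size and imbalance are all unknown, so the documents do not support saying that alcohol will mask a drug effect, only that it could go undetected if it did.

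The statement of one reading per period rests on Appendix 1 and concerns spirography. Section 9.3 places videotaped TETRAS at Visits 1 to 3, and section 8 refers to efficacy measures within each study visit. Those passages need reconciling with Appendix 1.

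**What to change.** - **Visits 4 and 8.** Add to section 9.3 that subjects take no alcohol from the day before the visit until that visit's tremor measures are done. Record the time of last alcohol and of last usual tremor medication. If alcohol was taken, rebook within the ±3-day window that Appendix 1 already allows.
- **Visit 0.** Only record last alcohol intake, after consent. Section 12 allows no study procedure before consent, and consent is taken at this visit, so a restriction the day before is not possible. The shared baseline cancels in the drug-placebo contrast in any case.

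The cost is one sentence in the visit instructions, a short question at three existing visits, an occasional rebooked visit and a minor burden on subjects. The sample size is unchanged. The recorded times would also allow a sensitivity analysis that leaves out affected readings.

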11. RECRUITMENT AND PROCEDURES PREPARATORY TO RESEARCH

Subjects will be recruited primarily through print and online advertising (advertisement language is also attached for approval) with the assistance of the International Essential Tremor Foundation and the local UCSD Movement Disorders clinic. In addition, we would request a partial waiver of individual authorization for use of Protected Health Information (PHI) by the IRB as this component meets the requirements outlined by the HIPAA Privacy Rule, 45 CFR 164 section 512(I). Specifically, we would request a waiver pertaining to targeted EMR queries of UCSD Epic to identify individuals with Essential Tremor and collecting the following variables: name, contact info, birthdate, diagnosis of essential tremor, presence of parkinson's disease (as an exclusion variable), and use of primidone. Data from the EMR query will be used to inform treating physicians that they may have eligible patients and to assist in making patients aware of the study. We will not contact patients directly without having received prior consent to be contacted.

12. INFORMED CONSENT

Interested patients and their caregivers will be scheduled to meet with a qualified investigative staff member and receive an explanation of the study purpose and requirements in lay language. If still interested in participating after receiving an explanation of the study, patients and their caregivers will be given an opportunity to review and inquire about the study-specific written informed consent form. Patients and their caregivers will have ample time to think about the information in the written informed consent form and have a chance to discuss it with family members or other people. Any patient and caregiver who has difficulty understanding the information contained in the written informed consent form will be asked to reread the misunderstood portion(s) of the consent and discuss it with a research staff member until s/he shows complete understanding of the information discussed in the informed consent form, and may thus give full consent. Research staff will work closely with patients and their caregivers' questions must be answered fully by trained and qualified staff. Any patient or caregiver who is unable to demonstrate understanding of the information contained in the information form will be excluded from study participation.

Prior to a patient's participation in the study, the written IRB approved informed consent form will be signed and personally dated by the patient) and by the person who conducted the informed consent discussion. In addition, a statement to document the informed consenting process will be recorded in the patient's source documents.

The consent form and any other information provided to patients will be revised whenever important new information becomes available that is relevant to a patient's consent and continued participation in the study. The revised consent form and information will receive IRB approval prior to use. The Investigator, or study coordinator should fully inform all patients of all pertinent aspects of the study and any new information relevant to the patients' willingness to continue participation in the study. This communication with the patient should be documented by the patient signing and personally dating the revised consent form and by written documentation of this discussion with the patient in the Investigator's study files available to Sponsor for onsite review.

Each patient who consents to participate in the study will receive a copy of the signed and dated written informed consent form and any other information provided to patients prior to the participation in the study. The original signed forms will be maintained in the Investigator's study file. After providing and documenting consent on the IRB approved written informed consent form, patients will be assigned their patient screening number and proceed to the Screening Period.

A copy of the informed consent and HIPAA form has been uploaded for review and approval.

The signed informed consent includes the following information:

- 1. Who is conducting the study
- 2. Procedures
- 3. Potential risks and discomforts
- 4. Benefits
- 5. Expense to subjects
- 6. Confidentiality
- 7. Voluntary participation/withdrawal
- 8. Emergency and study contact
- 9. HIPAA discussion

No study procedures will occur including screening until informed consent is obtained. The patient may withdraw his/her consent to participate in the study at any time. A patient is considered as enrolled in the study when he/she has signed the informed consent form. The entire consenting process will take place in a private exam room to ensure the participant's privacy and confidentiality is protected.

